4.4. Statistical Design and Power

4.4_Statistical_Design_and_Power.pdf

4.5. Subject Participation Duration

approximately 24 weeks

4.6. Will the study use an FDA-regulated intervention?

Yes No

4.6.a. If yes, describe the availability of Investigational Product (IP) and Investigational New Drug (IND)/Investigational Device Exemption (IDE) status

4.7. Dissemination Plan

4.7_Dissemination_Resource_Sharing.pdf

4.4 Statistical Design & Power

Design (see “Research Strategy”, Figure 7): Screened, eligible patients complete clinical, neurocognitive and functional measures and candidate biomarkers. In Test 1, all subjects are tested in Sound Sweeps after PBO, and then assigned to TCT+PBO vs. TCT+MEM arms (n=27/arm) using stratified random sampling (over sex, age and high/low Test 1 (baseline) APS learning) blind to arm identity, similar to¹⁰⁷. Stratifying for baseline APS learning should increase the sensitivity of the primary target engagement metric. An example of a table for arm assignment is seen here:

Gender	Baseline	Age	Group								
Male	High	< 39	PBO	PBO	MEM	MEM	MEM	MEM	PBO	PBO	PBO
	High	≥ 39	PBO	MEM	PBO	MEM	MEM	PBO	MEM	PBO	PBO
	Low	< 39	MEM	MEM	PBO	PBO	PBO	PBO	MEM	MEM	MEM
	Low	≥ 39	MEM	PBO	MEM	PBO	PBO	MEM	PBO	MEM	MEM
Female	High	< 39	PBO	PBO	MEM	MEM	MEM	MEM	PBO	PBO	PBO
	High	≥ 39	PBO	MEM	PBO	MEM	MEM	PBO	MEM	PBO	PBO
	Low	< 39	MEM	PBO	MEM	PBO	PBO	MEM	PBO	MEM	MEM
	Low	≥ 39	MEM	MEM	PBO	PBO	PBO	PBO	MEM	MEM	MEM

Example of table for stratified random sampling, by gender, baseline APS learning (post-PBO) and age (based on approximate mean age (39 yo) of last 100 SZ patients tested in our program)

Test 2 follows approximately 5-7 days later. Tests 1 and 2 are used to assess target engagement (Aim 1: MEM-enhanced APS learning) and MEM effects on auditory discrimination. Our design allows for 20% attrition from enrollment (n=69) to completion of target engagement testing (n=54).

For Aim 2, TCT is scheduled 3 d/week and continues until a subject completes 30-h (approximately 10-12 weeks). 60 min prior to each TCT session, patients take either PBO or 20 mg MEM, as per arm assignment. Patients and staff are blind to study arm; staff are blind to patients’ baseline or post-intervention assessments. Outcome measures are assessed after sessions 10, 20 and 30, and 12 weeks post-TCT. See “Research Strategy” for details.

General Statistical Approach: Hypothesis tests are 2-sided ($\alpha=.05$). Type I error is controlled by selecting optimal *a priori* targets for primary analyses; secondary analyses use false discovery rate corrections. When appropriate, missing data are handled via multiple imputation or full information maximum likelihood estimation. Expected drop-out rates and ways to minimize them are described in the parent application.

Differential drop-out rates from PBO vs. MEM arms are monitored. Clinical follow-up is pursued with all patients exiting the study through post-TCT week 12.

Cohort differences: For between-subject contrasts (drug), baseline demographic, clinical, antipsychotic/anticholinergic load and performance differences are tested and used as covariates if indicated. Sex differences are tested for all measures.

Procedures for Alternative or Unexpected Results: Linear mixed-effects models allow for the analysis of all available data using an intent-to-treat approach. This approach, however, assumes that data are missing at random. A potential concern is nonrandom dropout, particularly when dropout is related to the (missing) outcomes; that is, not missing at random. To make the missing at random assumption more plausible, we will explore the use of auxiliary variables. Auxiliary variables are covariates that predict both dropout and outcomes. By adding

auxiliary variables to our models, nonrandom dropout is corrected by conditioning treatment effects on the predictors of dropout.

Primary Efficacy Endpoint(s): Aim 1: Target engagement – APS learning will be significantly greater under MEM vs. PBO conditions. Aim 2: Pilot trial - Compared to PBO arm patients, MEM arm patients will exhibit greater clinical benefit, as indicated by one or more of the following: greater, faster or more durable improvements in PANSSt (reduced scores; see below, "Go/No-Go"), MCCBc (increased scores) or WHODAS (reduced scores).

Secondary Efficacy Endpoint(s): Aim 3: Biomarkers - baseline levels of specific neurocognitive or EEG-based measures, or changes in specific measures with initial MEM exposure, predict greater sensitivity to MEM-enhanced neurocognitive, clinical or functional gains over 30 sessions of TCT.

Analyses testing primary and secondary hypotheses will include all subjects' clinical, neurocognitive and functional assessments. Data from subjects who do not complete the full study are carried forward in an "intent to treat" design, and their data are analyzed using linear mixed models. Separate analyses will compare completion / drop-out rates across arms, as well as a 14-item 7-point Likert scale assessing treatment satisfaction.

Go/No-Go decision and primary and secondary endpoints

"Go/No-Go" decisions are based on traditional statistical significance (Aim 1) and effect sizes (Aim 2). Formal statistical testing is conducted using linear mixed-effects (LME) models; hypothesis tests are 2-sided ($\alpha=0.05$). Model parameters are estimated via the R lme4 package and Cohen's d is estimated via the EMAtools package. Type I errors are minimized by constraining the number of primary analyses; secondary analyses use false discovery rate corrections.

PANSSt scores will be assessed at specific intervals. Because TCT is associated with improvements in both positive and negative symptoms, our *a priori* hypothesis is that a PACT effect will be evident in both positive and negative symptoms. Hence, PANSSt is used as the primary metric of symptomatic gains. A greater reduction in PANSSt score will be detected using data from baseline through TCT 30h, by a significant main effect of group (arm) or a significant interaction of group x session, with post-hoc contrasts revealing significant group differences at TCT 30h. A faster reduction in PANSSt scores will be detected using these same data by a significant interaction of group x session and a significant group difference at a point prior to TCT 30h. A more durable reduction in PANSSt scores will be detected using data from TCT 30h through 12 weeks post-TCT, by a significant main effect of arm or a significant interaction of group x post-TCT day, with post-hoc contrasts revealing significant group differences 12 weeks post-TCT.

Comparable analytic approaches will be used for neurocognition (MCCBc) and function (WHODAS) as described in "Research Strategy". Data will be described as means with SEM. Tests for normalcy will be applied to all data and non-parametric comparisons will be used if normalcy is not demonstrated. The Analysis Set for these data will be all subjects who have completed 30h of TCT and post-TCT clinical, neurocognitive and function assessments. When appropriate, missing data are handled via multiple imputation or full information maximum likelihood estimation.

Secondary regression analyses assess the predictive value of putative biomarkers on clinical, neurocognitive or functional gains from the addition of MEM to TCT. Future studies with larger samples will assess potentially more informative models, e.g. Path Analysis to study moderating effects of APS MEM sensitivity and biomarkers on both indirect (moderated-mediation) and direct paths between treatment and outcome.

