Outcome and “Go Decisions”. In addition to confirming “target engagement”, this application tests the hypothesis that SZ patients given MEM +TCT will exhibit greater, faster and/or more durable improvements (change from baseline) in symptoms, neurocognition and/or function compared to patients given PBO+TCT, and that this enhanced clinical response will be associated with greater MEM-enhanced TCT learning.

The small “n” necessitated by the 3-year timeline and demanding treatment schedule greatly constrains the total number of outcome measures.

Moreover, the plan to assess not only magnitude but also rate and durability of PACT gains triples the number of primary analyses. Thus, we selected only one **primary** clinical, neurocognitive and functional outcome measure (Table 1) – recognizing that they are relatively “blunt” metrics - but will track several other, more focused, measures as well as inter-measure correlations in exploratory analyses to inform future studies.

A “Go” decision requires: 1) confirmation of target engagement (APS learning, MEM>PBO, p<0.05); 2) evidence of gains from PACT ($d \geq 0.5$ (MEM > PBO)) in primary clinical, neurocognitive and/or functional measures (Table 1), and 3) the absence of adverse effects of MEM that are significantly greater than PBO levels. The decision to not use traditional statistical significance as “Go” criteria for Aim 2 reflects this RFA’s call for “Pilot” studies, the need to identify candidate treatments for a subsequent larger “n” Confirmatory Efficacy R01 study, and the limits in sample size resulting from the 3-year R33 duration. Cohen defined a medium effect size ($d=0.5$) as one that is “visible to the naked eye,” and this amount of change is viewed as clinically meaningful in trials targeting negative symptoms.⁹⁹⁻¹⁰¹ This $d=0.5$ “Go” threshold for Aim 2 corresponds to a “number needed to treat” (NNT) value ≈ 3.62 . While a “Go” decision does not require identification of a biomarker predicting greater PACT sensitivity (Aim 3), the identification of one or more meaningful predictors that could be incorporated into a Confirmatory Efficacy trial would favorably impact a “Go” decision.

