 - drug group x session interaction ($p<0.05$) followed by MEM+TCT > PBO+TCT at specific session # or combination;
4. **More durable** clinical, neurocognitive **or** functional gains:
 - MEM+TCT > PBO+TCT at post-TCT week 12.

PANSSt: *Positive & Negative Symptom Scale total*; MCCB-C: *MATRICS Composite*; Fnxn: *Function (assessed via the World Health Organization Disability Schedule 2.0 (WHODAS))*

Rhythm Recall: Subjects listen to and replicate a short rhythmic sequence. This task is designed to stimulate both basic auditory processes supported by primary auditory cortex, and non-verbal auditory WM.

Symptoms are assessed to track clinical status and TCT response. TCT reduces positive symptoms of psychosis, and we predict that MEM will augment these effects via enhanced TCT learning (i.e. not via a lasting direct pharmacological effect of MEM), detected by the Positive & Negative Syndrome Scale. For this reason, and based on the need to limit total outcome measures, **PANSS Total Score is the primary clinical outcome measure**. Positive and negative symptom subscales, as well as PANSS factor-derived measures, will be assessed in exploratory analyses. Other secondary clinical measures will include: 1) Psychotic Symptom Rating Scales (PSRS; assesses auditory hallucinations); 2) Young Mania Rating Scale; 3) Patient Health Questionnaire-9 (PHQ-9; current depressive symptoms); 4) Abnormal Involuntary Movement Scale (AIMS); 5) **C-SSRS**; “Lifetime/Recent version” at screen; “Since Last Visit” at follow-up visits). The C-SSRS is a reliable, valid and sensitive measure of suicidal ideation⁹⁸; *any “yes” in C-SSRS prompts an immediate full evaluation/action plan by a study M.D.; and* 7) MEM Cessation Symptom Assessment (ACSA).

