Post-treatment protocol: On completion of 30 TCT sessions, participants will be offered the option of maintaining their assigned drug (PBO or MEM) through the 22-week durability assessments. Those who opt to discontinue the study drug will titrate off, over a 3-week period. After week 22, study blind will be broken, and subjects who continued to receive MEM will again be offered the option of titrating off of MEM vs. maintaining MEM treatment coordinated with, and under the supervision of, their primary provider.

Data Analysis: “Go/No Go” decisions are based on traditional statistical significance (Aim 1) and effect sizes (Aim 2). Formal statistical testing is conducted using linear mixed-effects (LME) models; hypothesis tests are 2-sided ($\alpha=.05$). Model parameters are estimated via the R lme4 package and Cohen’s d is estimated via the

EMAtools package. Type I errors are minimized by constraining the number of primary analyses; secondary analyses use false discovery rate corrections. Expected attrition rates are described above. Because outcome measures involve a “change from baseline”, baseline metrics are compared between PBO and MEM arms, and any baseline differences are addressed in the outcome analyses. Differential drop-out rates from PBO vs. MEM arms are monitored. Data are assumed to be missing at random; full information maximum likelihood estimators are used, and all data/cases are included in analyses. Clinical follow-up is pursued with all patients exiting the study through post-TCT week 12. Cohort differences: For between-subject contrasts (main effect of drug), differences in age, antipsychotic and anticholinergic loads are tested and used as covariates^{2,33,95}. Sex differences are tested for all measures. NIH Data Harmonization: 3 “PhenX Toolkit” (NOT-MH-15-009) measures of function are used; see above and “Resource Sharing Plan”.

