Subject “throughput”: We will enroll and screen 23 subjects/yr, test target engagement in 18 subjects/yr, and (conservatively) complete TCT training in 12 subjects/yr. This will yield 2 “target engagement” Aim 1 arms of n=27, and (conservatively) 2 TCT completion Aim 2 arms of n=18. Training capacity (2 TCT stations with morning and afternoon sessions on M, W and F, with T and Th “make-up” days for missed appointments, 48 weeks/year) allows for a “maximum throughput” of 19.2 subjects/yr. To reach the target of **12 TCT-completing subjects/year**, we would need to maintain training rates of **62.5% capacity**. This is well within our historical testing levels.

Power analyses: Consistent with the FOA, this study will adequately power tests of target engagement (Aim 1) for traditional significance, while the “Go” signal for therapeutic impact (Aim 2) is based on effect size ($d=0.5$). To detect target engagement for an LME model with $d=0.5$, 80% power, alpha=0.05, test-retest correlation=0.8, and a linear treatment effect, n=27 randomized participants are required per Hedeker et al (1999). This is a conservative estimate of d for target engagement, since empirically, d for target engagement with 20 mg MEM was 0.85 (Fig. 3). A future Confirmatory Efficacy trial will be powered to apply more robust approaches to Aim 2, e.g. Path Analysis⁶⁰ to study moderating effects of APS MEM sensitivity and biomarkers on both indirect (moderated-mediation) and direct paths between treatment and outcome.

Innovative ideas raise questions. Here are some answers:

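### Section 4.4 says covariate adjustment corrects non-random drop-out, which it cannot do for drop-out driven by unseen outcomes, and it leaves open adjustment for predictors measured after randomisation

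*Combined protocol and SAP*

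**What the plan says.** The main analysis is a linear mixed model. The Research Strategy (Data Analysis) states "Data are assumed to be missing at random" and relies on full information maximum likelihood. Section 4.4 (General Statistical Approach, and again under the Go/No-Go heading) allows multiple imputation or full information maximum likelihood where appropriate.

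Under Procedures for Alternative or Unexpected Results, section 4.4 accepts that this assumption may fail, "particularly when dropout is related to the (missing) outcomes; that is, not missing at random". Its response is: "To make the missing at random assumption more plausible, we will explore the use of auxiliary variables". It then defines the tool, "Auxiliary variables are covariates that predict both dropout and outcomes", and concludes that once these are added to the models "nonrandom dropout is corrected by conditioning treatment effects on the predictors of dropout".

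The variables are not listed, and nothing says they must be measured before randomisation. Drop-out rates are to be compared between arms. Neither the Research Strategy nor section 4.4 gives an analysis that departs from missing at random, such as a delta-adjusted, pattern-mixture or selection-model analysis.

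**The concern.** There are two separate difficulties.

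First, the paragraph begins with data that are not missing at random and ends by saying the problem is corrected. Conditioning on observed predictors makes missing at random more credible. It does nothing about the part of drop-out that depends on outcomes nobody saw. This holds whether the predictors are baseline or later ones.

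Second, the stated mechanism is to condition the treatment effect itself on the predictors. That is harmless for a variable the drug cannot have changed. It is not harmless for one measured after study drug has started, and this trial's own hypothesis supplies a candidate. For symptoms the Research Strategy says "we predict that MEM will augment these effects via enhanced TCT learning". Early learning could plausibly predict both staying in training and benefiting from it. Placed beside treatment, it would absorb part of the pathway under test, and the coefficient would no longer be the total drug effect.

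What is at stake is Aim 2. Its Go rule compares an effect size with d = 0.5 and mostly does so without a significance test, so a shift in the estimate feeds straight into the decision if the affected estimate is the one used.

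**Working it through.** **1. The plan's own figures.** Subject throughput gives 12 TCT completers a year over a 3-year study: 12 × 3 = 36, or 18 per arm. With 27 randomised per arm, 27 − 18 = 9 may not complete, and 9/27 = 33%. The plan calls this conservative. It gives no figure for any auxiliary variable, so the inputs below are assumptions.

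**2. What auxiliaries can and cannot repair.** The simulation has 1,000,000 patients per arm, one auxiliary A unaffected by drug, a correlation of 0.5 between A and outcome within arm, a true effect of 0.50 SD, and one-third drop-out per arm. Where drop-out is selective, its log-odds fall by 1 per SD of the variable driving it.

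| Drop-out depends on | No auxiliary | A as covariate | A modelled jointly |
|---|---|---|---|
| A, MEM arm only | 0.64 | 0.50 | 0.50 |
| Unseen outcome, MEM arm only | 0.78 | 0.71 | 0.72 |
| Unseen outcome, PBO arm only | 0.22 | 0.29 | 0.28 |
| Unseen outcome, same form in both arms | 0.50 | 0.50 | 0.50 |

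Row 1 shows the method working when A explains the drop-out. In rows 2 and 3 the bias with no auxiliary is 0.28, and 0.21 remains after adjustment (0.71 − 0.50, or 0.50 − 0.29), which is about three quarters. With correlations from 0.3 to 0.7, joint modelling still gave 0.76 to 0.65 (MEM arm selective) and 0.24 to 0.35 (PBO arm selective). Row 4 is a limit on the point: equal selection in both arms left the contrast unbiased in this model.

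**3. Conditioning on a predictor the drug changes.** Let a be the drug effect on A in SD units and ρ the within-arm correlation of A with outcome, both with within-arm SD 1 and A scored so that higher is better. If the total effect is 0.50, the treatment coefficient with A in the model is

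0.50 − ρ × a.

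No drop-out is needed for this shift. Dividing by the residual SD, √(1 − ρ²), gives d on that scale (in brackets).

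| a | ρ = 0.3 | ρ = 0.5 | ρ = 0.7 |
|---|---|---|---|
| 0 (baseline variable) | 0.50 | 0.50 | 0.50 |
| 0.2 | 0.44 (0.46) | 0.40 (0.46) | 0.36 (0.50) |
| 0.35 | 0.395 (0.41) | 0.325 (0.375) | 0.255 (0.36) |
| 0.5 | 0.35 (0.37) | 0.25 (0.29) | 0.15 (0.21) |

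Worked corners: 0.50 − 0.3 × 0.2 = 0.44 and 0.50 − 0.7 × 0.5 = 0.15.

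The sign can reverse. If MEM worsens a predictor whose worsening harms outcome, a is negative. With a = −0.2 and ρ = 0.5 the estimate is 0.50 + 0.10 = 0.60.

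**4. The alternative.** In the same simulation, with drop-out depending on A, joint modelling of A and outcome returned 0.50 for every combination of a and ρ tried.

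**The case against.** The strongest reply is that the plan never says the auxiliaries will be post-randomisation. Where section 4.4 names covariates, under Cohort differences just before this paragraph, they are baseline characteristics and medication load. For such variables the method removes no drug effect and repairs whatever drop-out they explain. The use is exploratory, sits under a contingency heading, and is introduced with the sound aim of making missing at random more plausible. All of this stands, and it confines the second difficulty to a risk left open.

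A reader might infer that the plan as written would push a true effect below the Go threshold. The documents do not support that. Aim 2 takes its Go estimate from the mixed-model drug or drug-by-session effect, and nothing says an auxiliary-adjusted estimate replaces it. Early PANSS change, an obvious candidate predictor, is already a modelled outcome for PANSS through sessions 10 and 20, which is the proper handling.

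A reader might also take 33% non-completion to mean 33% missing data. Under the intent-to-treat wording, partial completers contribute their session 10 and 20 data, and clinical follow-up is pursued in patients who leave. However, the Analysis Set sentence under the Go/No-Go heading counts only those who finish 30 hours and the post-TCT assessments. That needs reconciling with the intent-to-treat statement, since it would leave this method no drop-outs to handle.

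Finally, observed data cannot test missing at random, and a delta analysis cannot either. That is true, but it can show how large a departure would change the decision. None of these replies rescues the claim of correction.

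**Conclusion.** The statement that non-random drop-out is corrected is wrong as written. Auxiliaries remove the bias they explain and leave the remainder, and the plan has no analysis showing how much that remainder could matter. With selective drop-out in one arm the simulated estimate stayed well away from 0.50 in either direction. With equal selection in both arms it did not, so the size depends on a mechanism the documents cannot supply.

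The loss of drug effect through conditioning is conditional. It needs a post-randomisation auxiliary, a drug effect on it, and its entry beside treatment. The text permits this without stating it. The range of 0.44 to 0.15 SD rests on assumed inputs and one auxiliary with one endpoint. It is somewhat higher as d on the residual SD, zero bias for baseline variables, and inflation if the drug worsens a harmful predictor. It is not a prediction of what this trial will report.

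The change is worth making because a better method than the stated one is available and cheap.

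**What to change.** 1. Limit covariates in the treatment-effect model to variables measured before randomisation (baseline and Test 1), and list them in advance. Test 2 and later measures follow study drug and should not stand beside treatment.
2. Use any post-randomisation auxiliary only in the multiple-imputation model or as an additional outcome in a joint likelihood. Section 4.4 already names multiple imputation, so the route exists.
3. Replace the claim of correction with a statement that the missing-at-random assumption is made more plausible.
4. Add one delta-adjusted sensitivity analysis by arm for the Aim 2 Go endpoints: shift the imputed outcomes of drop-outs over a stated range (for example 0 to 0.5 SD) and report the shift at which the Go decision changes.

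The cost is SAP wording and a modest amount of extra analysis, with no new data and no change to trial conduct.

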Aim 1 – Confirm target engagement: The primary dependent measure of target engagement is MEM-enhanced APS learning. APS learning is defined as the reduction in Sound Sweeps APS threshold (ms) Test 1 to Test 2 assessment. Target engagement was demonstrated in Fig. 3⁷⁶, and will be confirmed if APS learning is increased by MEM (note that MEM and PBO groups are matched by Test 1 PBO performance via stratified randomized assignment). As appropriate, effect sizes and inferential statistics are based on standard regression or LME models with random intercepts. A significant interaction between contrast coded drug (PBO vs. MEM) and Test (Test 1 vs. Test 2) predictors on APS learning is a “Go” criteria and confirms target engagement.

Aim 2 – Test clinical, neurocognitive and functional impact of MEM on TCT, and its relationship to target engagement: We will determine if MEM+TCT produces greater, faster or more durable clinical, neurocognitive or functional gains from baseline, compared to PBO+TCT, over a 30-session course of TCT. A Cohen’s $d > 0.5$ for the main effect of drug (PBO vs. MEM) or drug x session (#10, 20, 30) interaction in an LME model is the primary “Go” criteria. The effect of drug assesses “greater” gains. Reverse Helmert contrasts for session assesses “faster” gains. A separate model comparing differences in outcomes at 12-weeks post-TCT assesses “more durable” gains. Secondary analyses will examine whether change in MEM-enhanced APS learning (“within-subject” target engagement; Aim 1) predicts gains in Aim 2 outcome measures.

Aim 3 – Biomarkers of MEM-induced gains: We will determine if baseline levels of specific neurocognitive or EEG-based measures, or changes in specific measures with initial MEM exposure (Test 2 vs. 1), predict greater sensitivity to MEM-enhanced neurocognitive, clinical or functional gains over 30-h of TCT. Regression analyses will assess whether specific candidate biomarkers predict MEM-enhanced gains in outcome measures.

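### The Aim 2 Go rule is an effect size in most of the plan, but Section 4.4 defines the same gains by significance, gives 'faster' a third definition, and leaves the SD behind d unnamed

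*Combined protocol and SAP*

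**What the plan says.** **Effect-size rule.** Research Strategy, Outcome and Go Decisions, sets the Aim 2 Go at d of at least 0.5 and explains why significance was not chosen. The Table 1 header asks for target engagement plus any one of three routes at d above 0.5. The Aim 2 paragraph of Data Analysis uses the same d threshold as Table 1 for its leading Go criterion; the wording there is "for the main effect of drug (PBO vs. MEM) or drug x session (#10, 20, 30) interaction in an LME model is the primary". Both power sections and item 10 of the questions and answers agree. Section 4.4 opens its Go/No-Go text the same way: "decisions are based on traditional statistical significance (Aim 1) and effect sizes (Aim 2".

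**Significance definitions.** The Aim 2 endpoint in Section 4.4 is a gain "as indicated by one or more of the following: greater, faster or more durable improvements in PANSSt (reduced scores; see below", which points to the Go/No-Go text. There, a greater gain is detected "by a significant main effect of group (arm) or a significant interaction of group x session, with post-hoc contrasts revealing significant group differences" at session 30. More durable gains are defined in the same style, and MCCB and WHODAS are to be handled comparably. No d appears in these definitions.

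**Faster gains, three versions.**
- Table 1, row 3: "drug group x session interaction ($p<0.05$) followed by MEM+TCT > PBO+TCT at specific session # or combination", under the table's d>0.5.
- Data Analysis, Aim 2: d above 0.5 for the interaction, where "Reverse Helmert contrasts for session assesses" faster gains; no p-value condition.
- Section 4.4: "a significant interaction of group x session and a significant group difference at a point prior to TCT 30h"; no d.

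**Smaller differences.** For durability, Table 1 has "MEM+TCT > PBO+TCT at post-TCT week 12" and Data Analysis has a separate 12-week model, while Section 4.4 models session 30 through 12 weeks. The threshold is d≥0.5 in Outcome and Go Decisions but d>0.5 in Table 1 and Data Analysis. For d itself, the plan names a software package but no standardising SD.

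**The concern.** The Go decision is the main product of this pilot. If the texts differ, the same data can give Go under one section and no recognised gain under another, and the choice could be made after the results are known. The pass rate when there is no clinical benefit also depends on which text is followed. The plan states no such rate for Aim 2. It says only that type I error is controlled (Section 4.4, General Statistical Approach) or minimised (Data Analysis and the Go/No-Go text) through the choice or number of primary analyses. Yet the Go rule can be passed on any of three outcomes by any of three routes, and Outcome and Go Decisions notes that the three routes triple the primary analyses.

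**Working it through.** **Inputs from the documents.** Two-sided alpha 0.05; Aim 2 threshold d=0.5; 27 randomised per arm (power analyses); 18 completers per arm expected (Subject throughput). Section 4.4 supports either number, because it includes all subjects in one place and only 30-hour completers in another. Using 27 assumes complete data.

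**1. The plan's own figure.** For Aim 1 it gives d=0.5, 80% power, test-retest correlation r=0.8 and n=27 per group. With d on the raw-score SD and analysis of change, the SD of change is √(2(1−0.8)) = 0.632 raw SDs. Then n = 2(1.960+0.842)²×0.4/0.25 = 25.1, so 26 per arm. With the t distribution, 26 gives 79.8% and 27 gives 81.4%, so 27 is reproduced. Post-test only (63) and ANCOVA (23) do not reproduce it. The one worked figure therefore uses the raw SD, but it concerns Aim 1.

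**2. Significance cut-off for one contrast, d on the SD of change.** Critical d = t(0.975, 2n−2)×√(2/n).
- n=18: 0.677. Observed d=0.5 gives p=0.14.
- n=27: 0.546. Observed d=0.5 gives p=0.07.

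With true d=0.5 on this scale (noncentral t), d≥0.5 is met in 50% of trials at either n. Significance is met in 31% (n=18) or 44% (n=27). The two rules disagree in about 20% or 7%.

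**3. The same cut-off, d on the raw SD.** Multiply by √(2(1−r)):

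| r | n=18 | n=27 |
|---|---|---|
| 0.5 | 0.68 | 0.55 |
| 0.65 | 0.57 | 0.46 |
| 0.8 | 0.43 | 0.35 |

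At r=0.8, observed d=0.5 gives p=0.024 (n=18) or 0.005 (n=27). Every d≥0.5 on a single change contrast is then significant, and the mismatch reverses: some significant results fall below d=0.5.

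**4. Chance of passing Aim 2 with no clinical effect, given target engagement and acceptable safety.** This was simulated with three outcomes, baseline plus sessions 10, 20, 30 and week 12, and complete data. Assumed, not in the documents: (baseline–follow-up, follow-up–follow-up) correlations (0.5, 0.5), (0.5, 0.8), (0.65, 0.8) and (0.8, 0.8); between-outcome correlation 0 or 0.5. Greater means session-averaged change at d≥0.5, and durable means week-12 change at d≥0.5. Versions of faster:

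| Faster | SD of change, n=18 | SD of change, n=27 | Raw SD, n=18 | Raw SD, n=27 |
|---|---|---|---|---|
| Session-10 or -20 d≥0.5, no p gate | 28–44% | 17–26% | 8–41% | 2–24% |
| Reverse Helmert contrast d≥0.5, sign favouring memantine | 45–56% | 27–34% | 8–48% | 2–27% |

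In the SD-of-change columns the Helmert contrast is standardised by its own SD. On the SD of change, the Table 1 gate (interaction p<0.05 plus session-10 or -20 d≥0.5) gives 23–34% (n=18) or 13–20% (n=27). Section 4.4's significance definitions give 8–15% at either n.

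**5. If neither aim has an effect.** Aim 1 must also pass in the favourable direction (0.025). Taking the aims as independent, 0.025×0.434 = 0.011 (no gate) and 0.025×0.561 = 0.014 (Helmert), so about 1%.

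**The case against.** The strongest defence is that Section 4.4 does not change the Go rule. Its first sentence bases Aim 2 on effect sizes, its second turns to formal testing, and its heading covers endpoints as well as Go/No-Go. The significance text can then be read as endpoint tests. A reader might infer that Section 4.4 makes significance a condition of Go; it never says so, and Outcome and Go Decisions expressly declines it. That much stands. But no sentence makes the separation, and the endpoint text points the reader to the Go/No-Go passage. The defence also does not reach faster gains: Table 1 and the Aim 2 analysis text are both explicitly Go criteria, and they differ on the p-value condition.

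A second objection is that the size rests on one choice of SD. This also stands. With the raw SD and r=0.8, the range of d that is Go but not significant is empty for a single contrast, and false-Go rates fall to about 8–9% (n=18) or 2% (n=27). Nor is the Helmert version always the most permissive: on the raw SD with correlations (0.5, 0.8) and n=18 it gives 24–29%, against 27–34% with no gate.

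Third, the type I wording accompanies two-sided tests and need not describe the d rule, so to call it false goes too far. The plan also openly explains its pilot reasoning. That part of the point is secondary.

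**Conclusion.** The conflict in the text is established and rests on no numerical assumption. Faster gains have three definitions, two of them stated as Go criteria; durability has two models; and Section 4.4 leaves the role of its significance tests unstated. The prevailing intention, an effect-size Go, is clear, but it cannot be applied without choices that the plan does not make.

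The numerical consequence is conditional. On the SD of change, observed d from 0.50 up to 0.68 (n=18) or 0.55 (n=27) meets the effect-size rule without significance. On the raw SD with r=0.8 no such range exists for a single contrast. That convention reproduces the Aim 1 sample size, but its use for Aim 2 is an assumption.

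A reader might take the 28–56% range at n=18 as the trial's false-Go rate. It is not: it assumes the SD of change, target engagement, acceptable safety and complete data. The corresponding raw-SD range is 8–48%, and with no effect on either aim the overall rate is about 1%. The conditional case still matters, because the plan itself says that target engagement may occur without clinical gain. This should be fixed; confidence is high on the wording and limited on the size.

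**What to change.** - In Section 4.4, state that the Aim 2 Go rests on d, with one threshold (≥ or >) used throughout and reported with its 95% CI, and that the significance tests there are endpoint analyses and not Go conditions.
- Give one definition of faster in Table 1, the Aim 2 analysis text and Section 4.4: whether interaction p<0.05 is needed, which contrast counts and which sign. Do the same for more durable.
- Name the SD that standardises d and the contrast for each route.
- Say that the type I error wording refers to the formal tests. For the Go rule, state the conditional false-Go probability, simulated for the exact rule, SD and analysis set adopted.

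The choice on the p-value gate should be made with its effect in view: on the SD of change at n=18, dropping it moves the rate from 23–34% to 28–44%. The cost is wording and a small simulation, with no change to data collection. The stated decision properties may look less favourable.
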